The association between psychosis and RBD in PD is well established (4), as both have been correlated with a more widespread distribution of alpha-synuclein in the nervous system (5). In addition, sleep fragmentation, vivid nightmares, and RBD have been associated with the presence of hallucinations (6). It is therefore a common occurrence for PD patients with visual hallucinations and concomitant sleep disturbance to present to the practitioner seeking therapeutic help.

Traditional pharmacologic treatments for RBD are melatonin and clonazepam, which suffer from a lack of good evidence for their use, and are not completely effective in eliminating the symptoms of RBD (7, 8). In addition, clonazepam has risks particularly in elderly patients such as confusion and somnolence, and as a benzodiazepine, may be associated with an increase in cognitive decline and falls (9, 10). Quetiapine, an atypical antipsychotic with sedative properties, is often used in PD patients to treat both visual hallucinations and insomnia, but had no effect on sleep times as measured by PSG in a double blind study (11). Sleep fragmentation is often treated with similarly sedating medications. Even in patients with early stage disease who suffer from sleep problems, these drugs can cause unwanted side effects, particularly over-sedation or daytime sleepiness. Clearly, better treatments are needed for PD patients with sleep disorders.

One potential therapeutic opportunity exists with the relatively new drug pimavanserin. Pimavanserin is an inverse agonist at serotonin 5-HT_{2A} receptors that was approved by the FDA in 2016 for the treatment of psychotic symptoms in patients with PD (12). Limited evidence exists that pimavanserin may have a beneficial effect on sleep. Participants taking pimavanserin as part of the Phase III randomized controlled trial of psychosis in PD reported an improvement in nighttime sleep as detected by the SCOPA-NS sleep scale (13). In addition, pimavanserin has been shown to affect sleep architecture on polysomnography (PSG), particularly to increase slow wave sleep and decrease awakenings in healthy adults (9). Therefore pimavanserin presents an opportunity for a potentially new pharmacologic treatment of sleep disorders in PD patients with psychotic symptoms, and perhaps for all PD patients who suffer from sleep disruptions.

Given the lack of previous research in this area, a pilot study is proposed in order to gather preliminary data regarding the effect of pimavanserin on sleep quality in this patient population. Since sleep is a complex phenomenon, its assessment will integrate quantitative and subjective measures, namely PSG and a series of validated questionnaires.

Hypothesis:

The proposed study is feasible in terms of its design and recruitment, and will provide preliminary data regarding the effect of pimavanserin on sleep parameters in patients with PD psychosis for development of a larger trial.

This is a feasibility study to help generate hypotheses. It is not powered for statistical significance. Our study size is limited by the financial resources available to us.

Primary objective: To determine whether there is any evidence that pimavanserin has a beneficial effect on subjective and objective measures of night-time sleep in patients with PD psychosis.

Secondary Objectives

To inform the prospective feasibility of the current study design in terms of recruitment and retention.

Inclusion criteria:

- 1) Has a diagnosis of idiopathic PD according to UK PD Society Brain Bank diagnostic criteria
- 2) Has a history of hallucinations or delusions associated with PD
- 3) Has a history of sleep disturbance
- 4) Is between the ages of 40 and 85
- 5) Has been on a stable dose of all PD medications for at least 30 days prior to enrolment

Exclusion criteria

- 1) Has evidence of an atypical or secondary parkinsonian disorder
- 2) Has a contraindication to taking pimavanserin
- 3) Has contraindication to PSG
- 4) There has been a change to patient's neuropsychiatric medications including dopaminergic medications (Sinemet, dopamine agonists, MAO-B inhibitors), SSRIs, SNRIs, dopamine-blocking agents, anti-epileptics, anticholinergics, or benzodiazepines for at least 30 days prior to enrollment
- 5) Has traveled through 3 or more time zones within 60 days prior to study screening
- 6) Patient is a night-shift worker

Primary endpoint:

Evidence of a change pre and post- drug treatment in sleep architecture as seen on PSG in terms of 1) REM Sleep without atonia (RSWA) 2) number of arousals

Secondary endpoints:

- 1) A change in other PSG parameters pre and post-treatment including:
 - a) Sleep latency
 - c) wake after sleep onset
 - d) total sleep time
 - e) sleep efficiency
 - f) time in each sleep stage (N1 N2 N3, REM)
- 2) Change in qualitative sleep and RBD self-assessments (RBDSQ, PDSS-2 and PFS-16).
- 3) Recruitment and adherence rates

Trial Design check boxes: Other

If other, please specify:

This study uses a self-control design. A similar design was used to study the effect of LCIG on sleep in PD (14).

At baseline/screening and after 6 weeks of treatment with pimavanserin, the following assessments will be completed:

- i) Polysomnography (PSG)
- ii) Sleep questionnaires:
 - a. Parkinson's Disease Sleep Scale, 2nd version (PDSS-2)
 - b. Parkinson's disease Fatigue scale (PFS-16)
 - c. RBD sleep questionnaire (RBDSQ)
 - d. MDS Unified Parkinson's disease rating scale (MDS-UPDRS)
 - e. The Montreal Cognitive assessment (MOCA) (administered at baseline/screening only)

At baseline/screening, the following study will be done:

- i) EKG

Study Phase:

If Other, please specify: Pilot study

Number of Sites: 1

Sample size justification/Statistical Analysis:

Estimated number of patients: 10 patients will be enrolled from SUNY Downstate Health Sciences University. As this is a pilot study, there are no formal sample size calculations and power estimates. Estimating a drop-out rate of 10% due to adverse effects as seen in previous studies with pimavanserin (15), we will aim to recruit and enroll a total of 10 patients (our budget therefore assumes a total of 10 patients). If necessary, more participants will be added

to maintain a total of 10 participants with complete data.

Study drug related issues:

The standard dose of Pimavanserin (Nuplazid) 34mg capsules oral daily will be used in this study. Patients will be treated for 6 weeks in keeping with prior studies to ensure adequate treatment duration (12). Using the above estimate for number of patients to be enrolled: 1 tablet per day x 10 patients x 42 days = 420 capsules will be requested.

Estimated Duration of study:

Year 1

Months 1-3: Administrative set-up, IRB submission and approval, set up screening protocols, role out study awareness within the recruiting hospitals, subject recruitment

Months 4-12: Subject enrollment and ongoing recruitment

Goal 50% enrollment by end of year 1

Year 2

Months 1-6: Subject enrollment

Months 7-9: Complete all study visits and subject follow-up; clean, edit, and lock study database

Months 10-12: Data analyses, manuscript preparation and submission

Study visits procedures:

Visit 1 – Screening/Baseline

- 1) Informed Consent
- 2) Screening for inclusion/exclusion criteria
Vital Signs (blood pressure, pulse, height and weight)
medical history, personal information (date of birth, gender, race/ethnicity) and medications taken (including over-the-counter)
- 3) Clinical Evaluation
 - a. Parkinson's Disease Sleep Scale, 2nd version (PDSS-2)
 - b. Parkinson's disease Fatigue scale (PFS-16)
 - c. RBD sleep questionnaire (RBDSQ)
 - d. MDS Unified Parkinson's disease rating scale (MDS-UPDRS)
 - e. The Montreal Cognitive assessment (MOCA) (administered at baseline only)
 - f. EKG
- 4) Dispense study drug if a patient is eligible for the study
- 5) A subject will be scheduled for Polysomnography (PSG), sleep study, at United Sleep Diagnostics, Inc.
PSG records the changes that occur during sleep, e.g., number of arousals, sleep latency, wake after sleep onset, total sleep time, sleep efficiency, time in each sleep stage.

The PSG monitors brain activity (EEG - electroencephalography), eye movements (EOG - electrooculography), muscle activity (EMG - electromyography), and heart rhythm (ECG - electrocardiography)

A subject will report to the United Sleep Diagnostics located at [name] at 8 pm on the scheduled date for the sleep study and stay overnight.

A sleep technician will attach the electrodes (metal discs) to a subject's skin and monitor a subject during the study.

The report will be sent to the study doctor for analysis.

Visit 2 - Baseline PSG (same day as Screening/Baseline)

- 1) Polysomnography will be done at United Sleep Diagnostics clinic
- 2) Start study drug Day 1

Visit 3 - Phone Call Week 2

- 1) Phone visit with Study coordinator to evaluate how a study participant tolerates the study drug and how it is affecting his/her Parkinson's symptoms; review of current medications

Visit 4 - Follow-up PSG Week 6

- 1) Polysomnography

Visit 5 -Week 6 (same day as PSG)/Early Withdrawal

- 1) Clinical Evaluation
 - a. Parkinson's Disease Sleep Scale, 2nd version (PDSS-2)
 - b. Parkinson's disease Fatigue scale (PFS-16)
 - c. RBD sleep questionnaire (RBDSQ)
 - d. MDS Unified Parkinson's disease rating scale (MDS-UPDRS)
- 2) Return of empty study drug bottle and unused study drug

A study participant will be reimbursed after Visit 2 Baseline PSG of \$200 (\$50 for Visit 1 Screening/Baseline; \$150 for Visit 2 Baseline PSG). Then a study participant will be reimbursed after Visit 5 6 weeks/Early Withdrawal of \$350 (\$150 for Visit 4 Follow-up PSG 6 weeks; \$200 for Visit 5 6 weeks/Early Withdrawal).

A check will be mailed to a study participant.

If a study participant leaves the study early, he/she will be reimbursed only for visits that he/she completes.

A plan to monitor conduct of the study at the site

Because this is Investigator-Initiated study, the PI/sponsor-investigator, [name] understands her responsibility for oversight of the study, and takes responsibility for any unanticipated problems or serious or continuing non-compliance;
attends a study “kickoff” meeting;
will be responsible for reporting any reportable events that occur;
conducts site initiation visit with all study staff to provide any needed training on study protocol;
is responsible to address any issues that arise;
will conduct conference calls with all study staff; agenda and minutes will be recorded and filed;
will assess all SAEs.

Investigator comments:

[name] and her study team have extensive experience in academic clinical research. [name] completed her fellowship at Columbia University under the tutelage of [name]. During her fellowship she also received instruction in clinical trials research from [name]. Her first academic faculty position was at Yale University where she was mentored by [name], who has an extensive publication record in the field of movement disorders. Currently, she works closely with [name], the Vice-Chair of Neurology at SUNY Downstate Health Sciences University and a nationally recognized researcher. [name] is currently involved in clinical research at SUNY Downstate Health Sciences University, including a translational research project funded by the Michael J. Fox Foundation, and a multi-site clinical drug trial for PD. In addition, her scholarship encompasses mentoring resident physician research and forging collaborations with faculty. To further strengthen the study team, two additional academic neurologists in the field of movement disorders and sleep medicine with proven track records in clinical research will be consulted to help guide the study set-up and manuscript publication.

Please note that the clinical portion of this study will take place at SUNY Downstate Health Sciences University Neurology Department. The sleep study will be performed at the United Sleep Diagnostics lab.

The study will be advertised on the e-screens around the SUNY Downstate Health Sciences University campus.

There is no intent to seek a new indication for the drug.

To Report all adverse events directly to the FDA in accordance with applicable law and Study protocol.

AE / SAE Reporting: All serious adverse events (SAE) must be reported to Acadia Call Center at [name] within 24 hours of such SAE.

A copy of any reports to the FDA (e.g. SUSAR) will be sent to Acadia at the time of submission to the FDA.

All complaints (product complaints or product grievances), regardless of origin, must be reported to the Acadia Call Center at [name].

Describe support:

None

Planned Publications: Does pimavanserin improve sleep in patients with Parkinson disease psychosis? A pilot study

SUPPORT:

Funding Support: Acadia Pharmaceuticals, Inc.

Product Request: [name]; [contact]

Legal/contracting information: [name]; [contact]

Shipping Site information:

[name]

SUNY Downstate Health Sciences University

[name]

Pharmacy Department

[name]

References

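### The second primary endpoint is a raw count of arousals with no hours-of-sleep denominator, so its pre/post change mixes fragmentation with sleep duration

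*Protocol*

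**What the plan says.** The Primary endpoint section of the protocol asks for evidence of a change from before to after treatment in sleep architecture "as seen on PSG in terms of 1) REM Sleep without atonia (RSWA) 2) number of arousals". No unit or denominator is attached to the arousals.

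The description of the sleep study under Study visits procedures (Visit 1, item 5) uses the same term and lists the duration measures taken from the same recording: "number of arousals, sleep latency, wake after sleep onset, total sleep time, sleep efficiency, time in each sleep stage".

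Secondary endpoints, item 1, is "A change in other PSG parameters pre and post-treatment including" a list that contains wake after sleep onset, sleep efficiency and "d) total sleep time". No direction of change is stated for any of them.

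On the length of the night, Visit 1, item 5 says only that the patient reports to the laboratory "at 8 pm on the scheduled date for the sleep study and stay overnight". Lights-out, lights-on and recording length are not given.

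On the comparison, the Trial Design section states "This study uses a self-control design", with one PSG at baseline and one at week 6. The sample size section gives 10 patients with no formal calculation.

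**The concern.** A patient who sleeps longer has more time in which to be aroused. If the arousal rate falls and sleep lengthens, both are improvements, yet the count can stay level or rise. If sleep shortens and the rate does not change, the count falls and looks like a benefit. The count alone cannot tell these cases apart.

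The protocol itself treats sleep duration as something that may change, since it makes three duration-related measures into change endpoints. The design offers no protection: there is one night before and one night after in 10 patients, with no concurrent control, so a difference in sleep time between the nights passes straight into the endpoint.

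At stake is how one of the two primary PSG measures is read. The primary objective asks whether the drug benefits night-time sleep, and the background names sleep fragmentation among the problems that motivate the study. The pilot is meant to supply preliminary data for a larger trial, and a change in the raw count would have to be rescaled before it could describe fragmentation there.

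**Working it through.** The protocol gives no arousal rate, sleep time, variance or expected effect, so it has no figure of its own to reproduce. Every change below is an assumption, shown as a range.

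**Inputs from the protocol.** The measure is a count (Primary endpoint). Total sleep time is recorded on the same PSG (Visit 1, item 5) and may change (Secondary endpoints, item 1). The comparison is within patient, baseline against week 6 (Trial Design).

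**Identity.** Count = arousals per hour of sleep × hours of sleep. With sleep time changing by a signed fraction g and the rate by r:

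change in count = (1 + g)(1 + r) − 1

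The baseline rate cancels, so the percentages hold at any starting value.

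**Break-even.** Setting the change in the count to zero gives r = −g/(1 + g) for a sleep gain g, and r = s/(1 − s) for a sleep loss s.

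| Size of sleep change | Gain: rate fall that is hidden | Loss: rate rise that is hidden |
|---|---|---|
| 10% | 0.10/1.10 = 9.1% | 0.10/0.90 = 11.1% |
| 20% | 0.20/1.20 = 16.7% | 0.20/0.80 = 25.0% |
| 30% | 0.30/1.30 = 23.1% | 0.30/0.70 = 42.9% |

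**Change in the count, by change in sleep time (columns) and true change in the rate (rows).**

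| Rate | −20% | −10% | 0 | +10% | +20% |
|---|---|---|---|---|---|
| +10% | −12% | −1% | +10% | +21% | +32% |
| 0 | −20% | −10% | 0% | +10% | +20% |
| −10% | −28% | −19% | −10% | −1% | +8% |
| −20% | −36% | −28% | −20% | −12% | −4% |

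With equal sleep time the count and the rate agree. Away from that column the count can have the wrong sign: a 10% fall in the rate with 20% more sleep gives 1.20 × 0.90 − 1 = +8%, and a 10% rise in the rate with 20% less sleep gives 0.80 × 1.10 − 1 = −12%.

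**The same in arousals per night (assumed 15 per hour and 5 hours, so 75).**

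- Six hours at an unchanged rate: 15 × 6 = 90, a rise of 20%.
- Four hours at an unchanged rate: 15 × 4 = 60, a fall of 20%.
- Six hours with the rate down 15%: 12.75 × 6 = 76.5, a rise of 2%, although the index fell from 15 to 12.75.

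**Illustration at n = 10.** 20,000 paired trials were simulated. All inputs are assumed: median rate 20 per hour with between-patient log-SD 0.4, sleep time with mean 5 h and SD 1 h, night-to-night SD 1 h, log-SD 0.15 in the rate each night, and Poisson counts.

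| True rate | Mean sleep change | Trials with lower mean count | Trials with lower mean index |
|---|---|---|---|
| unchanged | −1 h | 97% | 50% |
| unchanged | +1 h | 4% | 50% |
| −15% | 0 | 94% | 97% |
| −15% | +1 h | 43% | 97% |

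This shows the mechanism at the planned size. It does not predict what will happen in this trial.

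**The case against.** The strongest reply is that the endpoint line names constructs rather than metrics. RSWA in the same sentence has no unit either, the wording for arousals may be shorthand, and an SAP or scoring manual could define it per hour. That is possible, but nothing in the protocol says so. For arousals the protocol does state a scale, a number, and repeats it in the description of the PSG. If it is shorthand, the same one-line clarification is needed.

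A second reply is that arousals per night is a legitimate quantity, and that the index also moves with duration: with the count fixed and sleep 20% longer, the index falls 1 − 1/1.20 = 16.7% without one arousal removed. The arithmetic is right, but this is what less fragmentation per hour of sleep means. It argues for reporting the count beside the index, not for making the count primary.

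Three points stand:

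- The index removes only the proportional effect of duration. It does not adjust for a changed mix of sleep stages, and the background cites increased slow wave sleep in healthy adults taking this drug.
- The 8 pm sentence is patient logistics. Both recordings are made at one laboratory, which may well have standard times. Even so, a fixed recording window would not settle the matter, because sleep within the window still varies.
- The consequence is modest. Total sleep time is reported anyway, no test or go/no-go rule hangs on the count, and the index can be computed afterwards.

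**Conclusion.** The point holds. As written, the second primary measure cannot by itself show whether sleep became less fragmented. Over assumed changes in sleep time of 10% to 30%, the count hides a fall in the rate of 9.1% to 23.1% when sleep lengthens, or a rise of 11.1% to 42.9% when it shortens. The protocol states no effect of the drug on total sleep time, so the direction and size of the distortion in this trial are unknown. If sleep time is the same on both nights there is none.

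The algebra needs no assumption beyond the definition of a rate; only the size of the sleep change is assumed. In an unpowered, hypothesis-generating pilot this is a moderate defect that loses no data. It is still worth correcting, because settling the scale of a primary measure before the data are seen is better than choosing it afterwards.

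**What to change.** Reword primary endpoint 2 as the change in the arousal index, defined as the number of arousals divided by the hours of total sleep time on the same PSG. Report the raw count as a descriptive measure, with total sleep time and time in each sleep stage beside it so that a reader can see what drives any change.

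The cost is one line of protocol wording. Arousals and total sleep time are already recorded on both nights, so no new data, procedures or patients are needed.

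### Does the visit schedule leave the baseline sleep recording exposed to a first dose, and does it reverse the order of questionnaires and PSG at Week 6?

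*Protocol*

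**What the plan says.** All the timing statements are in the Protocol, mostly under Study visits procedures.

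- **Visit 1 (Screening/Baseline).** After consent, screening, questionnaires and EKG, item 4 reads "Dispense study drug if a patient is eligible for the study". Item 5 says that a PSG will be booked at an outside sleep laboratory, where the patient reports "at 8 pm on the scheduled date for the sleep study and stay overnight".
- **Visit 2.** The heading is "Visit 2 - Baseline PSG (same day as Screening/Baseline"). It has two numbered items: the PSG first, then "Start study drug Day 1".
- **Visits 4 and 5.** Visit 4 is the Week 6 PSG. The next heading is "Visit 5 -Week 6 (same day as PSG)/Early Withdrawal", and that visit holds the repeat questionnaires and the return of study drug.
- **Primary endpoint.** "Evidence of a change pre and post- drug treatment in sleep architecture as seen on PSG", in terms of REM sleep without atonia and number of arousals.
- **Trial design.** "This study uses a self-control design". Assessment times are given as follows: "At baseline/screening and after 6 weeks of treatment with pimavanserin, the following assessments will be completed".

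**The concern.** There is no control group and the target is 10 patients, so each patient's one baseline night is the only comparator for the primary endpoint. If a capsule is taken before or during that night, the patient has no true pre-treatment value, and no later analysis can restore it.

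Three features of the schedule invite the worry. The patient holds the drug before going to the laboratory. The start of drug sits within the same visit as the recording, which begins in the evening and ends on the next calendar date, so Day 1 could be either date. And Visit 1 speaks of a scheduled date while Visit 2 says the same day, which looks like two different answers. The background section cites PSG effects of the drug in healthy adults (more slow wave sleep, fewer awakenings), so a dosed baseline would tend to understate the change.

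The second worry concerns the secondary endpoints. By visit number, the sleep and fatigue scales come before the PSG at baseline (Visits 1 and 2) and after it at Week 6 (Visits 4 and 5). If the Week 6 scales were completed after a night in the laboratory and the baseline scales were not, part of the change in PDSS-2 and PFS-16 could reflect that night and not the drug.

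**Working it through.** The Protocol gives no figure to reproduce here. The check is mainly a comparison of passages, followed by a look at the attenuation arithmetic.

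**1. Date of the baseline PSG.** Visit 1 item 5 fixes an arrival time (8 pm) on a date to be booked. The Visit 2 heading says which date: that of screening. A patient screened in clinic during the day and recorded from 8 pm that evening meets both statements. They would conflict only if the laboratory slot were on another day, which departs from the Visit 2 heading.

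**2. Recording and first dose.** Four statements bear on this.

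| Where | What it implies |
|---|---|
| Visit 1, item 4 | Drug is handed over; no intake is mentioned |
| Visit 2, items 1 and 2 | PSG listed first, start of drug second |
| Primary endpoint | Comparison of before with after drug |
| Trial design, assessment times | PSG at baseline/screening and after 6 weeks of treatment |

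None directs or permits intake before the recording, and the last three point to a recording made before treatment. Handing over the drug is separate from starting it, since the start has its own item at a later visit. Day 1 is undefined, but it is attached to the start of drug and so can be read as the first day of intake. On that reading it does not have to be the calendar date of screening.

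**3. Questionnaires and PSG at Week 6.** Visit 5 is on the same day as the PSG, and the PSG arrival time described at Visit 1 is 8 pm. The clinical part takes place at the university's neurology department and the PSG at a separate laboratory. A clinic visit earlier on the day of an 8 pm arrival would reproduce the baseline order. A visit the next morning would reverse it. The text allows the first and does not require the second, so the accurate statement is that the order is not fixed.

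**4. Size of a possible dilution.** Let the true mean change be d. Suppose m of 10 baseline nights follow a dose and each already shows a fraction f of the effect. The expected measured mean change is

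[(10 − m)·d + m·(1 − f)·d] / 10 = d·(1 − m·f/10).

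- m = 3, f = 0.5: 3 × 0.5 / 10 = 0.15, a 15% loss.
- m = 5, f = 1: 5 × 1 / 10 = 0.50, a 50% loss.
- m = 0, the schedule followed as listed: no loss, whatever f is.

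The algebra is right, but m and f are both assumptions and no passage supports a value above zero for m. The 50% case needs half the patients to dose against the listed order, and needs a first dose to produce the whole effect. That sits badly with the Protocol's own reason for treating for 6 weeks, which is to allow an adequate duration.

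**The case for a change.** The strongest case for a change is that list order is not a timing rule. The recording runs overnight. If staff read Day 1 as the screening date, the first capsule falls before or during the recording; if they wait until it is complete, Day 1 is the following date, which the text does not say. The patient arrives at an outside laboratory already holding the drug, and no stated safeguard stands in between. Visit sequence belongs in a protocol, and an analysis plan could not repair a baseline recorded on drug. On the questionnaires, the payment text supports the numbered sequence: the $150 for Visit 4 and the $200 for Visit 5 are paid together, as $350, after Visit 5. Drug return at Visit 5 also marks it as the closing visit.

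Part of this stands. No sentence says outright that the recording precedes the first dose, Day 1 is undefined for a night spanning two dates, and the order within the Week 6 day is open. But the objection needs staff to read Visit 2 against its own numbering and against the purpose of a baseline recording in a before-and-after study. Payment after the last visit shows when the money is sent; it does not show which of two same-day events came first. If the order at Week 6 did differ, it would touch secondary scales in an uncontrolled pilot, where any change already mixes the drug with everything else that differs between the two time points. The Protocol gives no basis for sizing that contribution.

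**Conclusion.** The concern does not hold as a defect in the plan. The two statements on the PSG date are compatible. The numbered items of Visit 2, the primary endpoint and the stated assessment times all describe a baseline recording made before treatment. The reversed questionnaire order is a possibility left open by the numbering and is not established by the text.

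The residue is a gap in wording that the site can fill sensibly from the listed order. Followed that way, the dilution of the primary endpoint is zero; the 15% and 50% figures describe departures from the schedule under assumed inputs. The study is also described as a feasibility pilot for generating hypotheses, without power for formal testing, so no confirmatory conclusion depends on this detail.

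This conclusion rests on two assumptions: that staff follow the order of items within Visit 2, and that the PSG takes place on the screening day as its heading says.

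### The PSG visit reveals off-drug or on-drug status, yet the protocol neither masks the scoring of RSWA and arousals to visit nor says who scores

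*Protocol*

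**What the plan says.** Under Trial Design the protocol states "This study uses a self-control design", so there is one arm and each patient is compared with himself or herself. The Primary endpoint is the pre/post change in RSWA and number of arousals on PSG. Other PSG measures, including time in REM sleep, are secondary.

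There are two recordings per patient. Visit 2 lists the baseline PSG and then the start of drug on Day 1. The second is "Visit 4 - Follow-up PSG Week 6".

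On the making and handling of a recording, Study visits procedures (Visit 1, item 5) says that a technician at the outside sleep laboratory attaches the electrodes and monitors the patient, and then: "The report will be sent to the study doctor for analysis". The same item describes the output by example: "PSG records the changes that occur during sleep, e.g., number of arousals, sleep latency, wake after sleep onset, total sleep time", followed by sleep efficiency and sleep stages. RSWA is not among the examples. The protocol names no scorer and mentions no masking, coding of recordings or reading order.

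**The concern.** Scoring RSWA and arousals requires judgement on the trace. Someone who knows which night is on drug may, without intending it, read the two nights differently. In a randomised trial with both arms read alike, such a shift between visits would largely cancel. Here it cannot cancel, because the estimate is the within-patient change itself.

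The data are meant to show whether there is any sign of benefit and to inform a larger trial. PSG is also the quantitative half of an assessment whose other half is self-report, so its value depends on its being read independently of expectation. Who reads, and what they know, is a matter of conduct that has to be settled before reading starts. It is not a detail that an SAP would usually supply.

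**Working it through.** The protocol gives no test, alpha, effect size or SD, so there is no stated figure to reproduce. The check has two parts.

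**1. What the text settles and leaves open**

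- *Does visit reveal treatment?* Yes. There is one arm, and Visit 2 (PSG listed before the first dose) is followed by Visit 4 (Week 6 on drug).
- *Is any reader masked to visit?* No such provision appears.
- *Who scores?* Not stated. A report comes from the laboratory, which suggests laboratory scoring, but it goes to the study doctor for analysis. For arousals the examples of PSG output point to the laboratory. For RSWA there is no pointer either way.
- *What would each reader know?* The study doctor, as a member of the trial team, would know the visit. What the laboratory knows is not stated.
- *Is there an expected direction?* The background cites fewer awakenings in healthy adults. That bears indirectly on arousals and not on RSWA.

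**2. Illustration of scale**

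Input from the protocol: n = 10 complete pairs ("to maintain a total of 10 participants with complete data"). Assumed: no true drug effect, a shift d in units of the SD of the paired change, a 95% interval, and a two-sided 5% paired t-test.

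Half-width of the 95% interval = t(0.975; 9 df)/√10 = 2.262/3.162 = 0.715 SD.

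Probability of nominal significance = P(|T| > 2.262), where T is noncentral t with 9 df and noncentrality d√10.

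| Assumed shift d | d / 0.715 | d√10 | Nominally significant |
|---|---|---|---|
| 0 | 0% | 0 | 5.0% |
| 0.1 | 14% | 0.316 | 5.9% |
| 0.2 | 28% | 0.632 | 8.8% |
| 0.4 | 56% | 1.265 | 20.5% |

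The figures are the same for a shift in either direction. A small shift would matter little at this sample size; one near 0.4 SD would clearly distort the result. Nothing in the protocol says which is closer to the truth.

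**The case against.** The strongest reply is that this is silence and not an error. The quoted sentence is neither wrong nor contradicted elsewhere, and scoring workflow may sit in a laboratory manual that is not shown. What stands of this is that the finding must be put as an open point. It remains a point for the protocol, because the protocol does describe how PSG results are handled and stops short of the step that produces the primary endpoint.

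Four stronger inferences are tempting and should be resisted.

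- *That the investigator scores unmasked.* A report, not a recording, leaves an outside laboratory, so the laboratory may well be the scorer. The absence of RSWA from a list of examples proves nothing.
- *That the result will be biased in favour of the drug.* No bias is documented, and no direction is supported for RSWA.
- *That the false-positive rate is 8.8% or 20.5%.* The study is declared hypothesis-generating and fixes no test, and the shifts are assumed. These figures show scale and nothing more.
- *That masking would make the change attributable to the drug.* It would not. First-night effects, regression to the mean and time effects are untouched.

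Two further objections limit the remedy. RSWA is scored within REM sleep, so masking only the two primary endpoints while staging stays open would be incoherent; the whole recording must be scored masked. And leaving a visit-labelled routine report in place would call for a second read, in a study limited by its funds. Masked scoring should therefore be the only scoring. The neurologists mentioned under Investigator comments are brought in to advise on set-up and publication, so the text does not support counting on them as readers.

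**Conclusion.** The point holds in a limited form. Visit coincides with treatment status, the protocol does not mask scoring to visit, and it does not say whether the laboratory or the study doctor scores. A visit-linked reading shift would enter the primary change unit for unit, with no control arm to offset it. Its size and direction are unknown: from negligible at 0.1 SD to more than half the confidence half-width at 0.4 SD, both assumed.

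Open-label treatment does not require open reading, so the gap can be closed at little cost. It is a worthwhile improvement and does not undermine the pilot. The conclusion rests on the baseline PSG being recorded before the first dose, as the order of items under Visit 2 implies, and on the laboratory being able to code and hold recordings, which the protocol does not address.

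**What to change.** Add to Study visits procedures, Visit 1, item 5, and apply to both PSG visits:

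- The sleep laboratory codes each recording and removes visit label and date.
- One laboratory scorer who did not attend those nights scores the whole recording (staging, RSWA and arousals together) under one scoring rule, in random order, once both nights of a participant are available.
- This is the single scoring used for all PSG endpoints.
- The study doctor receives the scored values after both nights are final. Any urgent safety observation is passed on as usual.

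If this is not feasible, name the scorer and state in the report that reading was not masked to visit.

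**Cost.** No extra patients, visits or recordings are needed, and no extra read if this is the laboratory's only scoring. Ten complete pairs give 20 recordings to score. Coding covers slightly more, because drop-outs leave a baseline night. At the protocol's figure ("Estimating a drop-out rate of 10% due to adverse effects"), and assuming drop-outs are replaced and leave independently, expected enrolment is 10/0.9 = 11.1. The probability of at most 3 drop-outs before 10 completers is 0.966, so coding would cover about 20 to 23 recordings.

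**Downside.** Scored baseline values arrive about 6 weeks later. Eligibility as written does not depend on them. The last pairs must be read within Year 2 Months 7-9, which also hold cleaning and lock. If the last participant starts at the end of Month 6, about 13 − 6 = 7 weeks remain. A replacement starting after that would leave less: about 5 weeks if at Week 2 (13 − 8), about 1 if at Week 6 (13 − 12). Scoring each pair as it completes confines the pressure to the last pairs.

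**Limit.** A scorer might still guess the on-drug night from the sleep architecture, so masking reduces this source of bias but does not guarantee its removal.
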